5.3	Efficacy Evaluation.....	21
5.3.1	Analysis of Primary Endpoint	21
5.3.2	Analysis of Secondary Endpoints.....	21

5.4	Sensitivity Analyses	24
5.5	Safety Evaluation	24
5.6	Additional Analyses	24
5.7	Data Problems	25
5.8	Differences to Trial Protocol	25
6	Statistical Software.....	25
7	References.....	25

1 Introduction

This Statistical Analysis Plan (SAP) is based on the study protocol version 5.0 of 18.05.2023 and follows the guideline for statistical analysis plans (Gamble, et al., 2017).

Some aspects of the statistical methods and the study design are already described in the study protocol. This SAP aims to further specify the procedures and statistical methods applied during the analysis of the study data.

Analysis will not be conducted but supervised by the Institute of Medical Biometry and Epidemiology, University Medical Center Hamburg-Eppendorf.

The present study is part of a collaborative research center (CRC 289 Treatment Expectation: www.treatment-expectation.de/en/).

1.1 Background and Rationale

Antidepressant medication (AM) is established as evidence-based, guideline recommended treatment. However, prescription rates are rising (Schwabe et al., 2018) and many patients remain on medication for several years, despite guideline recommendations (Moore et al., 2009). Discontinuation is associated with elevated risk of discontinuation symptoms and recurrence (Henssler et al., 2019) and both are likely to be influenced by dysfunctional expectations (Rutherford et al., 2010). To support patients and physicians in deciding about initiating and discontinuing AM, knowledge about effective and safe ways to discontinue AM is needed. Until today, no study has explored the interplay of patients' expectation (i.e., placebo effects) and pharmacological effects of AM discontinuation. Disentangling their effects and interaction has important implications for understanding the mechanisms underlying discontinuation symptoms and thus, for the design of future interventions. Hence, we will investigate expectation (high vs. medium expectation induced by verbal instruction) and pharmacological factors (discontinuation of AM vs. continuation) within a balanced open-hidden discontinuation trial.

1.2 Study Objective

This study aims to disentangle pharmacological from expectation effects and their interaction during discontinuation of antidepressants and explore their underlying processes. More specifically the following questions and hypotheses were stated:

- How do treatment and treatment expectation contribute to discontinuation symptom load? Treatment (discontinuation of AM vs. continuation) and treatment expectation (high vs. medium) interact in modulating discontinuation symptom load among remitted major depressive disorder (MDD) patients over the course of the experimental phase.
- In what way can discontinuation symptom load be affected by treatment expectation, i.e. the placebo-effect, alone? Remitted MDD patients who remain on their antidepressant medication will show a higher discontinuation symptom load with moderate than with high expectation.
- In what way can the discontinuation symptom load be affected by pharmacological factors alone? Remitted MDD patients with moderate treatment expectation will show a higher discontinuation symptom load if antidepressant medication is discontinued versus if antidepressant medication is continued.
- In what way does the discontinuation symptom load differ between high and moderate treatment expectation? Remitted MDD patients who discontinue their antidepressant

medication will show a higher discontinuation symptom load with high than with moderate treatment expectation.

- The relationship between treatment expectation and discontinuation symptom load will vary according to stress ratings, prior side effects of antidepressant medication, prior discontinuation experience, neuroticism, anxiety, somatosensory amplification, and illness framework.

1.3 Study Endpoints

1.3.1 Primary endpoint

Discontinuation symptom load over the course of the experimental phase (i.e., assessments from t2 till t9 will be considered and cover reported symptoms between week 2 until the end of week 13, adjusted for baseline symptoms reported at t1) assessed by the Discontinuation Emergent Signs and Symptoms Scale (DESS; Rosenbaum et al., 1998)

1.3.2 Secondary endpoints

- a) Discontinuation symptom load over the clinical observation period (i.e. assessments FU1 till FU3 will be considered and cover reported symptoms between the beginning of week 14 until week 52) assessed by the Discontinuation Emergent Signs and Symptoms Scale (DESS; Rosenbaum et al., 1998)
- b) Recurrence (yes or no) over the experimental period, i.e., appearance of a new depressive episode after full, sustained remission of depressive symptoms, will be monitored weekly during run-in and (dis-)continuation phase and biweekly during monitoring phase. Assessments from t1 till t9 will be considered and cover reported symptoms between week 1 until week 13, based on Beck Depression Inventory II and Montgomery Asberg Depression Rating Scale scores (BDI-II, Hautzinger et al., 2009; Montgomery-Asberg Depression Rating Scale [MADRS+], (Davidson et al., 1986; Schmidtke et al., 1988; Williams & Kobak, 2008). If recurrence is suspected (as indicated by BDI-II score >19 or MADRS score >21 over two study visits), corresponding SCID-5-CV sections will be conducted to (dis-)confirm recurrence (Beesdo-Baum et al., 2018; First et al., 2016).
- c) First recurrence over the course of the trial, i.e., appearance of a new depressive episode after full, sustained remission of depressive symptoms will be monitored weekly during run-in and (dis-)continuation phase, biweekly during monitoring phase, and at 26, 39, and 52 weeks post-baseline, as determined in a time-to-event analysis. Assessments from t1 till FU3 will be considered and cover reported symptoms between week 1 until week 52 based on Beck Depression Inventory II and Montgomery Asberg Depression Rating Scale scores (BDI-II, Hautzinger et al., 2009; Montgomery-Asberg Depression Rating Scale [MADRS+], (Davidson et al., 1986; Schmidtke et al., 1988; Williams & Kobak, 2008). If recurrence is suspected (as indicated by BDI-II score >19 or MADRS score >21 over two study visits), corresponding SCID-5-CV sections will be conducted to (dis-)confirm recurrence (Beesdo-Baum et al., 2018; First et al., 2016). Calendar week of start of new depressive episode will be examined and recorded.
- d) Difference in patient-reported stress between baseline at t1 and 12 weeks later at t9, assessed with the Perceived Stress Scale (PSS-10; Cohen et al 1983; Klein et al 2016)

- e) Difference in patient-reported state anxiety between baseline at t1 and 12 weeks later at t9, assessed with the two anxiety-related state subscales of the *State-Trait-Anxiety-Depression-Inventory* (STADI; Laux et al 2016; Renner et al 2018)
- f) Attentional and affective processing measured as bias scores (difference between reaction times) of happy versus neutral faces, sad versus neutral faces, and fearful versus neutral faces under high attention to faces in a modified emotional Posner task (Brassen et al., 2011)

1.3.3 Safety endpoints

- a) Self- and expert-rated depressive symptoms (BDI-II, Hautzinger et al., 2009; Montgomery-Asperg Depression Rating Scale [MADRS], (Davidson et al., 1986; Schmidtke et al., 1988; Williams & Kobak, 2008) including inspection of suicidality and recurrence
- b) Current treatment effects (Generic Rating Scale for Previous Treatment Experiences, Treatment Expectations, and Treatment Effects - Treatment Effects Subscale [GEEEffect], Rief et al., 2021)
- c) AEs (World Health Organization [WHO], 2000) including life events of subjectively high burden
- d) Clinical impression according to psychopathological findings

2 Study Methods

2.1 Trial Design

PHEA is a prospective, randomised, parallel-group, partly blinded, open-hidden discontinuation trial with a 2x2-factorial design. The allocation ratio is 1:1:1:1 for the four groups:

- Treatment discontinuation and high expectation - open discontinuation (OD):
Patients in this group receive gradually decreasing doses of prescribed AM in encapsulated tablets and will receive full information about their treatment (i.e., high expectation).
- Treatment continuation and high expectation - open continuation (OC):
Patients in this group remain on prescribed AM in identical encapsulated tablets and will receive full information about their treatment (i.e., high expectation).
- Treatment discontinuation and medium expectation - hidden discontinuation (HD):
Patients in this group will receive gradually decreasing doses of prescribed AM in encapsulated tablets and will be informed about a 50% chance of discontinuing versus remaining on AM (i.e., moderate expectation).
- Treatment continuation and medium expectation - hidden continuation (HC):
Patients in this group will remain on prescribed AM in identical encapsulated tablets and will be informed about a 50% chance of discontinuing versus remaining on AM (i.e., moderate expectation).

2.2 Randomization and Blinding

Stratified block randomization was used with variable block sizes.

Stratification variables were

- intake duration with 24 months as a marker for long-term intake (<24 months of AM vs. \geq 24 months, 3:7)
- risk of developing discontinuation symptoms associated with the antidepressant medication (moderate vs. higher or unknown risk, 1:1).

The script for the generation of a randomisation list was written by the responsible statistician of the IMBE and transferred to a study-independent employee of the IMBE who created the final randomization list using a new random seed.

The statistic software R (version 4.1.2) (R, 2021) and the package *blockrand* (Snow 2020) was used.

Randomization lists were handed to study staff who have no personal contact to study participants.

The staff responsible for analyses will be blinded with regard to group allocation. The study physician, the study psychologist, as well as supporting student assistants and the study participants are - in the case of assignment to one of the two hidden groups - blinded. Correspondingly, they are unblinded in case of assignment to one of the two open groups. The persons responsible for randomization are unblinded, but have no contact with the study participants. The study physician and the study psychologist are informed that the study participants have been assigned either to the (OD) open-discontinuation group, (OC) open-continuation group, or to one of the two hidden conditions, i.e. either (HD) hidden-discontinuation, or (HC) hidden-continuation. In this case, the study physician and the study psychologist have no knowledge of whether the study participant is in group (HD) or (HC). The information whether the participants belong to the groups (OD) or (OC), or to one of the two hidden groups (HD) or (HC), will be communicated by the study physician or the study psychologist.

2.3 Sample Size

A medium effect size of $f=0.22$, a significance level of $\alpha=0.05$, and a power of 80% were assumed. This resulted in 168 patients needed in total (i.e. 42 per group) using an ANOVA model (with main effects and interactions). Furthermore, with an expected drop-out rate of at most 15%, in total 196 patients need to be recruited (i.e. 49 per group).

Sample size calculation was conducted using G*Power (version 3.1.9.2).

2.4 Framework

Test for difference will be applied for all endpoints. The primary endpoint is tested in confirmatory manner. A significance level of 0.05 will be used. All secondary and safety endpoints will be analysed in an exploratory way and thus, no adjustment for multiplicity will be applied.

2.5 Statistical Interim Analyses and Stopping Guidance

No interim analysis is planned.

Criteria for individual study discontinuation will be reviewed during each study visit and, in case of monitoring, during each additional visit. If a participant falls acutely ill (e.g. Covid) during the discontinuation process, a physician may decide to extend the discontinuation process by the duration of the illness (max. 4 weeks). If so, the participant will continue to receive the currently administered dosage of medication from the study team. Measurements will be postponed accordingly and no additional interim measurements will take place. Study participation will be terminated in case of the patient's withdrawal of his/her informed consent, pregnancy, medical or psychological objections by the study physician or psychologist (i.e., severe depressive symptomatology, recurrence, suicidality, other serious or severe AEs, etc.), or insufficient compliance regarding the study participation or the medication. In these cases, the study physician informs about further treatment options and refers to other contact points in an interview. The continuation of the entire study will be questioned by the principal investigator in case of reoccurring AEs that might be causally related to the study treatment regimen, medical or psychological concerns by the study physician or psychologist, no or insufficient study activity (e.g. enrolment rate < 5 per year), or unforeseeable complications that do not justify study continuation. A safety board will monitor the study according to "Guidelines of Good Clinical Practice" (International Conference on Harmonisation of Technical Requirements for Registration of Pharmaceuticals for Human Use, 2015) and will meet regularly. See study protocol for decision path.

2.6 Timing of Outcome Assessments

See Table 1.

Table 1. Schedule of enrolment, intervention and assessments according to SPIRIT-PRO.

	STUDY PERIOD								
	Enrolment		Allocation	Experimental phase			Clinical observation		
Timepoint	S1	S2	t0	t1-t5	t6-t8	T9	FU1	FU2	FU3
Weeks	-2	-1	0	1/2/3/4/5	7/9/11	13	26	39	52
Enrolment									
Eligibility screen	✓	✓							
Informed consent			✓						
Initial consultation prescribing physician			✓						
Randomization				✓					
Interventions					✓	✓	✓		

Discontinuation versus continuation of AM High versus moderate expectation (open versus hidden treatment)			✓ ✓	✓ ✓	✓ ✓	
Assessment						
Primary outcome measures						
Discontinuation symptom load (DESS)		✓	✓	✓	✓	
Secondary outcome measures						
Discontinuation symptom load (DESS)					✓	✓
Recurrence			✓	✓	✓	✓
Psychophysiological stress (PSS-10)*		✓			✓	
State anxiety (STADI State)*		✓			✓	
Attentional, affective processing (Posner task)*					✓	
Possible modulators						
Psychophysiological stress (PSS-10)*		✓				
Side effects of antidepressant medication (GASE*)		✓			✓	
Prior discontinuation experience (GEEE _{PRE} *)		✓				
Personality traits (BFI-10)*		✓				
Trait anxiety (STADI State)*		✓				
Somatosensory amplification (SSAS)*		✓				
Illness perception (single item)		✓				
Further assessments						
Optional: rsfMRI		✓	✓ (t1)			
AM blood serum level			✓(t1)		✓	
Trait marker stress*		✓				
Adherence (single item)		✓	✓	✓	✓	✓
Self-reported depressive symptoms (BDI-II)*	✓	✓	✓	✓	✓	✓
Expert-rated depressive symptoms (MADRS)*	✓	✓	✓	✓	✓	✓
Prior discontinuation symptoms (DESS _{PAST})		✓				
Current treatment effects (GEEE _{ACT} *)		✓	✓	✓	✓	✓
Expectations (TEX-Q*)		✓	✓	✓	✓	✓
Expectations (GEEE _{EXP} *)		✓	✓	✓	✓	✓
Behavioral inhibition/approach (BIS-BAS scale)*		✓				
Psychopathology (SCID-5-CV interview)*	✓					
Well-being (SWEMWBS)		✓	✓	✓	✓	✓
Depression and Anxiety (PHQ-4)					✓	✓
Subjective Impairment (PDI*)		✓	✓(t1,t5)		✓	
Substance Use & Coping			✓(t1,t5)	✓(t7)	✓	
Screener Warmth & Competence*		✓	✓(t5)		✓	
Adverse events (single safety items)		✓	✓	✓	✓	✓
Suspicions about treatment (GEEE _{END})*					✓	
Demographic* & medical characteristics		✓			✓	✓
Debriefing & close-out						
Debriefing					✓	
Consultation prescribing physician					✓	
Individualized discontinuation plan for continuation groups						✓

Note. S1 = pre-screening; S2 = enrolment; t = assessment timepoint; FU = follow-up; AM = antidepressant medication; DESS = Discontinuation-Emergent Signs and Symptoms Scale; PSS-10 = Perceived Stress Scale, 10 item version; STADI = State-Trait-Anxiety-Depression-Scale, at t9 State only; GASE = Generic Assessment of Side Effects; GEEE_{PRE} = Generic Rating for Treatment Pre-Experiences, Treatment Expectations, and Treatment Effects (previous experiences); BFI-10 = 10-item Big-5 Inventory; SSAS = Somatosensory Amplification Scale; rsfMRI = resting-state functional Magnetic Resonance Imaging; BDI-II = Beck-Depression-Inventory II; MADRS = Montgomery-Asperg Depression Rating Scale; DESS_{PAST} = Discontinuation-Emergent Signs and Symptoms Scale (previous experiences); GEEE_{ACT} = Generic Rating for Treatment Pre-Experiences, Treatment Expectations, and Treatment Effects (treatment effects); TEX-Q = Treatment Expectation Questionnaire, 15 item version; GEEE_{EXP} = Generic Rating for Treatment Pre-Experiences, Treatment Expectations, and Treatment Effects (treatment expectations); BIS-BAS scale = Behavioral Inhibition and Approach System Scale; SCID-5-CV = Structured Clinical Interview for DSM-5; SWEMWBS = Short Warwick-Edinburgh Mental Well-Being Scale; PHQ-4 = Patient-Health-Questionnaire-4; PDI = Pain Disability Index (adapted to discontinuation symptoms); GEEE_{END} = Generic Rating for Treatment Pre-Experiences, Treatment Expectations, and Treatment Effects (suspicions about treatment); SPIRIT-PRO = Calvert M, Kyte D, Mercieca-Bebber R, Slade A, Chan AW, King MT, SPIRIT-PRO group (2018) Guidelines for inclusion of patient-reported outcomes in clinical trial protocols: the SPIRIT-PRO extension. *Jama*, 319:483-494. * Part of standardized psychometric test battery.

2.7 Timing of Final Analysis

Analyses might be conducted after completion of the respective study phase, as soon as all data of the respective endpoints are available. Therefore, the analyses of the endpoints concerning the

experimental phase, i.e. the primary analysis concerning discontinuation symptom load over the experimental phase and the analyses concerning the secondary endpoints recurrence over experimental phase, stress, state anxiety, and emotional and attentional processing will be conducted following completion of time point t9 (week 13 after randomization) and the corresponding data cleaning process (i.e. database has been reviewed for completeness and accuracy). According to our first projection, this will happen in the second quarter of 2024.

Analyses concerning the clinical observation phase of the study or the total study time, namely secondary endpoints discontinuation symptom load (during observational phase) and recurrence over the course of the clinical trial will be conducted following completion of FU3 (week 52 after randomization) and data cleaning process (i.e. database has been reviewed for completeness and accuracy). According to our first projection, this will happen in the first quarter of 2025.

3 Statistical Principles

3.1 Confidence Intervals and *P* Values

All applicable statistical tests will be two-sided and will be performed using a 5% significance level. All confidence intervals presented will be 95% and two-sided. Analyses of secondary and safety outcomes will be performed exploratory without adjustment for multiple testing.

3.2 Adherence and Protocol Deviations

Treatment adherence to intake of study medication during the experimental phase is assessed by a single item on the number of days the study medication was taken since the last study visit, as well as via blood analysis. Adherence to intake of study medication is defined as max. 1 omitted pill per week during the discontinuation period.

Major protocol deviations are:

- Non-adherence, i.e., more than 1 omitted pill per week during the discontinuation period, during the experimental phase
- Withdrawal of informed consent
- Pregnancy
- Insufficient compliance regarding requirements for the study participation

Minor protocol deviations are:

- If a participant falls acutely ill (e.g. Covid) during the discontinuation process, a physician may decide to extend the discontinuation process by the duration of the illness (max. 4 weeks). If so, the participant will continue to receive the currently administered dosage of medication from the study team. Measurements will be postponed accordingly; no additional interim measurements will take place.

3.3 Analysis Populations

3.3.1 Intent-to-treat (ITT)

The primary endpoint analysis is based on the intention-to-treat population, i.e. all randomized patients are included, as belonging to their randomization arm, regardless of whether they refused therapy, or whether other protocol violations are known.

3.3.2 Full analysis set (FAS)

For all secondary endpoints the full analysis set is used. FAS is as complete as possible and as close as possible to the ITT population. All available data will be used and all patients with available data will be included as belonging to their randomization arm, regardless of whether they refused therapy, or whether other protocol violations are known.

3.3.3 Per Protocol Population (PP)

The Per Protocol population is a subset of the ITT population and includes only patients who have no major protocol violation.

For the definition of major protocol deviations see Section 3.2.

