4.2 Eligibility

The number of ineligible patients randomised, if any, will be reported, with reasons for ineligibility. Ineligible patients are those who do not fulfil inclusion criteria or who show exclusion criteria:

Inclusion criteria

1. Adult patients (18-75 years) with fully remitted MDD, single or recurrent, as main diagnosis confirmed by prescribing physician and SCID-5-CV (Beesdo-Baum et al., 2018; First et al., 2016)
2. Intake of SSRI/SNRI (citalopram: 20-40mg, escitalopram: 10-20mg, sertraline: 75-150mg, venlafaxine: 75-150mg, duloxetine: 60-100mg, paroxetine: 20-40mg) or NaSSA (mirtazapine: 30-45mg)
3. Discontinuation wish by patient, supported by prescribing physician
4. Fulfilment of the German S3 national guideline recommendations for treatment of Major Depressive Disorders to discontinue AM: a) response to AM, b) symptom remission for at least four months (first episode)/ 2 years (2 or more episodes with significant functional impairment) and c) concurrent intake of antidepressant medication (at least 4 weeks on a steady dose)

Exclusion criteria

1. Acute or chronic somatic illness and/or intake of medication which might interfere with depressive disorder, AM or proposed study
2. Acute suicidality, psychotic symptoms, substance abuse or addiction within the last 12 months, current mania, or hypomania confirmed by SCID-5-CV or other psychopathology which might interfere with depressive disorder, AM or proposed study
3. Any history of bipolar disorder or psychosis confirmed by SCID-5-CV
4. Severe stressful life events (e.g., death of a family member) within six months prior to study participation
5. Insufficient German language proficiency.
6. No informed consent.

7. MRI-specific exclusion criteria, if applicable: phobic anxiety, claustrophobia, ferromagnetic implants, etc.

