4.3 Recruitment

A CONSORT (Schulz, Altman, & Moher, 2010) flow diagram will be used to summarise the number of patients (per treatment group where appropriate) who were:

- assessed for eligibility at screening
 1. fulfilling I/E-Criteria at screening
 2. not fulfilling I/E-Criteria at screening*
 3. post-hoc violation of I/E-Criteria*
- randomised
- not randomised*
- received the randomised treatment
- did not receive the randomised treatment*
- lost to follow-up*
- randomised and included in the primary analysis
- randomised and excluded from the primary analysis*

*reasons will be provided

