5.4 Sensitivity Analyses

In case of a violation of the normality assumption of the residuals, the primary analysis will be repeated with log transformed dependent variable, where appropriate.

Results of the post-hoc group comparisons will then be presented as adjusted mean factors with corresponding 95%- Wald confidence intervals (resulting from back-transformation of the adjusted mean differences) and p-values will be given.

The primary endpoint and the secondary endpoint a) will additionally be analyzed using the complete case data only, without adjustment for baseline discontinuation symptoms, and in the per protocol population.

Further sensitivity analyses on imputed data might be performed, see Section 5.2 for details. All endpoints might be analysed in the per protocol population.

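### The major deviations in Section 3.2 do not name a breach of the entry criteria, so the per-protocol set may retain randomised patients later found ineligible

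*SAP*

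**What the plan says.** Section 3.3.3 of the SAP gives the rule: "The Per Protocol population is a subset of the ITT population and includes only patients who have no major protocol violation". It then names its only source: "For the definition of major protocol deviations see Section 3.2".

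Section 3.2 opens its list with "Major protocol deviations are" and has no wording that marks the items as examples. There are four:

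- "Non-adherence, i.e., more than 1 omitted pill per week during the discontinuation period, during the experimental phase"
- withdrawal of consent
- pregnancy
- "Insufficient compliance regarding requirements for the study participation"

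Two other sections foresee ineligible patients. Section 4.2: "The number of ineligible patients randomised, if any, will be reported, with reasons for ineligibility". Section 4.3 gives "post-hoc violation of I/E-Criteria" its own line in the flow diagram, with reasons. Neither section ties these patients to an analysis set.

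Section 5.4 commits to analysing the primary endpoint and secondary endpoint a) on complete cases, "without adjustment for baseline discontinuation symptoms, and in the per protocol population". For the remaining endpoints a per-protocol analysis is optional.

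**The concern.** A per-protocol analysis is meant to show whether the result holds in patients who belonged in the trial and were treated as planned. The group hypotheses on symptom load in Section 1.2 concern remitted MDD patients, and full remission is part of the first inclusion criterion in Section 4.2. If a breach of entry criteria is not a major deviation, the per-protocol set is filtered on what patients did after randomisation but not on whether they should have been randomised. Agreement between the ITT and per-protocol results would then say less about the intended population than a reader would assume.

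This is not a detail that the SAP leaves to the protocol. The SAP defines both the set and the deviations itself, and points to its own Section 3.2.

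**Working it through.** **1. Compare the four items with the entry criteria.**

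| Item in Section 3.2 | What it concerns | Covers a breach of Section 4.2? |
|---|---|---|
| Non-adherence | Capsules omitted in the experimental phase | No |
| Withdrawal of consent | A decision by the patient | No |
| Pregnancy | A specific event | No |
| Insufficient compliance | Meeting the requirements of participation | Not by name; see step 2 |

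**2. Read the fourth item in context.** Section 2.5 gives almost the same phrase among the reasons for ending an individual's participation, where it refers to poor compliance with the study or the medication. That is conduct during the trial. Section 3.2 adds the words about requirements, so a reading that takes in the conditions for entry is possible, but it is not the natural one.

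**3. Follow one patient through the rules.** Suppose that a patient with a history of bipolar disorder (an exclusion criterion in Section 4.2) is randomised, takes every capsule and attends every visit. The history comes to light later.

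- Section 3.3.1: stays in ITT, which is correct.
- Sections 4.2 and 4.3: counted and reported with the reason.
- Section 3.2: no listed deviation applies on the natural reading.
- Section 3.3.3: stays in the per-protocol set.
- Section 5.4: enters the per-protocol analysis of the primary endpoint.

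**4. Precision cost of excluding such patients.** Inputs from Section 2.3: f = 0.22, alpha 0.05, power 80%, 168 evaluable patients (42 per group).

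Reproducing the plan's figure first: a 1-df effect in a four-cell ANOVA has noncentrality f² × N = 0.0484 × 168 = 8.13 with 1 and 164 degrees of freedom, which gives power 0.809. The smallest N with 80% power is 165, or 168 in equal groups. The stated figure is reproduced.

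The SAP gives no share of ineligible patients. The range below is assumed, for illustration:

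| Ineligible share | N left of 168 | Power at f = 0.22 |
|---|---|---|
| 0% | 168 | 0.81 |
| 2% | 165 | 0.80 |
| 5% | 160 | 0.79 |
| 10% | 151 | 0.77 |

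These rows count only the loss from ineligibility, not from the other deviations. On these assumptions the loss is small.

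**5. Bias from keeping them.** This would need the number of ineligible patients, their split over the four groups and their symptom scores. The SAP gives none of these.

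**The case against.** The strongest reply is that the compliance item may already cover eligibility, because requirements for taking part can include the criteria in Section 4.2. This stands in part: the wording is open enough that the gap cannot be called certain. But it does not rescue the rule, since two analysts could then build different per-protocol sets from the same text. Under Section 2.2 the study physician and psychologist know the allocation in the two open groups, so membership should not rest on an unwritten judgement.

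The second reply is that little depends on it. This largely stands. The confirmatory analysis is ITT, no decision rule uses the per-protocol result, Section 4.2 says only that ineligible patients will be reported if there are any, and two screening points with a structured interview make some breaches less likely.

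A third reply is that not every breach is equally serious, and that a rule covering all criteria also removes marginal cases. That is fair. If the trial team wants a narrower list, it can name the criteria that count, provided that it does so in advance.

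A reader might also infer a sizeable distortion. For a 2x2 interaction, f = 0.22 is a difference of differences of 4 × 0.22 = 0.88 SD. If 3 of 42 patients in one group were ineligible and scored 2 SD higher, the contrast would move by 3/42 × 2 = 0.143 SD, and 0.143/0.88 is about 16%. The document does not support this as an estimate:

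- The count, the excess and the clustering in one group are all invented. Eligibility precedes allocation, so randomisation gives no reason for clustering; equal numbers with equal excess in every group shift the interaction by zero.
- Even then the shift is less than half a standard error: sqrt(4/42) = 0.309 SD, and 0.143/0.309 = 0.46.
- The model in Section 5.3.1 adjusts for the DESS at t1, which would absorb part of any excess already present at that visit.

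**Conclusion.** The point holds as a badly fixed rule. On the natural reading of Sections 3.2 and 3.3.3, a compliant patient who should not have entered stays in the per-protocol set; on the alternative reading, the text is ambiguous. The per-protocol analysis that Section 5.4 commits to for the primary endpoint and secondary endpoint a) may therefore include patients outside the intended population.

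A reader might go further and say that the per-protocol check does not describe the trial population. That is too strong. If nobody ineligible is randomised, this gap changes nothing, and if a few are, the set is mixed and not wrong throughout. The ITT primary result is untouched. The size of any effect cannot be derived from the document. The conclusion rests on taking the list in Section 3.2 as complete, which its wording supports.

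**What to change.** Add a fifth item to the major deviations in Section 3.2: *violation of an inclusion or exclusion criterion in Section 4.2 that was present at randomisation (MRI-specific criteria excepted), classified before unblinding of the analysis staff*. Section 3.3.3 then excludes these patients without further change. ITT and FAS stay as they are.

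If the sponsor prefers to keep ineligible patients in the per-protocol set, Section 3.3.3 should say so and give the reason.

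The cost is one line of text and a slightly smaller per-protocol set. No new data are needed, because the breaches are already recorded for Sections 4.2 and 4.3, and the sample size does not change.
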